6.6.2. Deaths

The frequency (number and percentage) of participants in the safety analysis set who died, who died within 28 days after last dose of study treatment, who died after 28 days after last dose of study treatment as well as the primary reason for death, will be tabulated based on information from the 'Notice of Death' and 'Survival Follow-Up' CRFs.

The frequency (number and percentage) of participants in the safety analysis set who died within 30 days of first dose of study treatment will also be provided.

Date and cause of death will be provided in individual participant data listing together with selected dosing information (study treatment received, date of first/last administration).

6.6.3. Laboratory Data

Laboratory results will be converted to International System of Units (Système International d'unités, SI) units which will be used for applying toxicity grades and for all summaries. The number and percentage of participants who experienced laboratory test abnormalities will be summarized according to worst toxicity grade (CTCAE version 5.0) observed for each

laboratory assay. A shift summary of baseline grade by maximum postbaseline grade will be presented.

As described in [Section 3.4](#), baseline will be defined as the last assessment performed on or prior to date of the first dose of study treatment. If there are multiple assessments that meet the baseline definition on the same day without the ability to determine which was truly last, then the worst grade will be assigned as the baseline grade. Several of the CTCAE terms (including Hypo/Hypercalcemia, Chronic Kidney Disease, and Activated Partial Thromboplastin) can be derived using several laboratory tests (analytes).

Results collected as strict inequalities (eg, >10 , <10) will be converted to numeric values subtracting a factor of $<0.001>$. Expressions of the form " \geq " or " \leq " will be converted to the end point. These numeric values will be evaluated for clinically significant abnormalities, but will not be included in calculations of summary statistics.

Additionally, laboratory results will be programmatically classified according to NCI-CTCAE version 5.0 grade. Non-numerical qualifiers will not be taken into consideration in the derivation of grade (eg, hypokalemia Grade 1 and Grade 2 are only distinguished by a non-numerical qualifier and therefore Grade 2 will not be derived). In summary statistics the number and percentage of participants corresponding to grades that only include non-quantitative criteria will be displayed as a blank or NA (not assessed) rather than 0. If there is any overlap between grade criteria (eg, CTCAE grading criteria for Creatinine Increased – a value can fall into one range based on comparison to ULN and another range based on comparison to baseline), the highest (worst) grade would be assigned to that record. Grade 5 is defined in the CTCAE criteria guidance as an event with an outcome of death. Since laboratory data does not collect an outcome, Grade 5 is not used when programmatically grading laboratory data.

Grade 0 or Outside Toxicity Reference (OTR) is not defined specifically by in the CTCAE guidance. However, programmatically this is used as a category to represent those participants who did not meet any of the Grades 1 to 4 criteria. If the laboratory value is evaluable for CTCAE criteria grading (numeric value is present, valid units and ranges are present as required to allow conversion to standard units and grading), and does not qualify for any of the Grade 1-4 criteria for a given lab test, then the value is assigned as Grade 0 or OTR.

Several of the CTCAE terms (including Hypo/Hypercalcemia, Chronic Kidney Disease, and Activated Partial Thromboplastin) can be derived using several laboratory tests (analytes).

Abnormalities will be described using the worst grade by scheduled timepoint and overall. Worst grade by scheduled timepoint will be determined using local laboratory results. Worst case overall will be determined using local laboratory results from scheduled and unscheduled visits. Several laboratory tests have bi-directional grading criteria defined so that both low (hypo) and high (hyper) values can be graded separately. Each criterion will be summarized separately. In the cases where a value is graded as a Grade 1, 2, 3, or 4 for one

of the directions, that value will also be assigned as a Grade 0 for the opposite direction for that test. For example, a value meeting the criteria for Grade 3 Hypercalcemia will be classified as a Grade 0 Hypocalcemia. For CTCAE terms that can be derived using one of several laboratory tests, the maximum post-baseline grade for a given participant and CTCAE term will be the maximum across all possible laboratory tests.

Additional laboratory results that are not part of NCI-CTCAE will be presented according to the following categories by scheduled timepoint as well as overall: below normal limit, within normal limits, and above normal limits. In the unlikely event that for a given participant, clinically significant abnormalities are noted in both directions (eg, $>$ Upper Limit of Normal (ULN) and $<$ Lower Limit of Normal (LLN)), then both abnormalities are counted.

The following summary tables will be created:

- Shift summary of laboratory parameters during the on-treatment period by maximum CTCAE grade;
- Shift summary of laboratory parameters from \leq Grade 2 at baseline to \geq Grade 3 postbaseline;
- Shift summary of laboratory test results with no CTCAE criteria by worst on treatment assessment.

Liver function tests: Alanine aminotransferase (ALT), aspartate aminotransferase (AST), Alkaline Phosphatase (ALP), and total bilirubin (TBILI) are used to assess possible drug induced liver toxicity. The ratios of test result over the ULN will be calculated and classified for these three parameters during the on-treatment period.

Summary of liver function tests will include the following categories. The number and percentage of participants with each of the following during the on-treatment period will be summarized by treatment arm:

- $\text{ALT} \geq 3 \times \text{ULN}$, $\text{ALT} \geq 5 \times \text{ULN}$, $\text{ALT} \geq 10 \times \text{ULN}$, $\text{ALT} \geq 20 \times \text{ULN}$.
- $\text{AST} \geq 3 \times \text{ULN}$, $\text{AST} \geq 5 \times \text{ULN}$, $\text{AST} \geq 10 \times \text{ULN}$, $\text{AST} \geq 20 \times \text{ULN}$.
- $(\text{ALT or AST}) \geq 3 \times \text{ULN}$, $(\text{ALT or AST}) \geq 5 \times \text{ULN}$, $(\text{ALT or AST}) \geq 10 \times \text{ULN}$, $(\text{ALT or AST}) \geq 20 \times \text{ULN}$.
- $\text{TBILI} \geq 2 \times \text{ULN}$.
- Concurrent $\text{ALT} \geq 3 \times \text{ULN}$ and $\text{TBILI} \geq 2 \times \text{ULN}$.
- Concurrent $\text{AST} \geq 3 \times \text{ULN}$ and $\text{TBILI} \geq 2 \times \text{ULN}$.
- Concurrent $(\text{ALT or AST}) \geq 3 \times \text{ULN}$ and $\text{TBILI} \geq 2 \times \text{ULN}$.

- Concurrent (ALT or AST) $\geq 3 \times \text{ULN}$ and TBILI $\geq 2 \times \text{ULN}$ and ALP $> 2 \times \text{ULN}$.
- Concurrent (ALT or AST) $\geq 3 \times \text{ULN}$ and TBILI $\geq 2 \times \text{ULN}$ and ALP $\leq 2 \times \text{ULN}$ or missing.

Concurrent measurements are those occurring on the same date.

Categories will be cumulative, ie, a participant with an elevation of AST $\geq 10 \times \text{ULN}$ will also appear in the categories $\geq 5 \times \text{ULN}$ and $\geq 3 \times \text{ULN}$. Liver function elevation and possible Hy's Law cases will be summarized using frequency counts and percentages.

An evaluation of Drug-Induced Serious Hepatotoxicity (eDISH) plot will also be created, with different symbols for different treatment arms, by graphically displaying the following:

- Peak serum ALT(/ULN) vs peak total bilirubin (/ULN) including reference lines at ALT= $3 \times \text{ULN}$ and total bilirubin= $2 \times \text{ULN}$.
- Peak serum AST(/ULN) vs peak total bilirubin (/ULN) including reference lines at AST= $3 \times \text{ULN}$ and total bilirubin= $2 \times \text{ULN}$.

In addition, a listing of all TBILI, ALT, AST and ALP values for participants with a post-baseline TBILI $\geq 2 \times \text{ULN}$, ALT $\geq 3 \times \text{ULN}$ or AST $\geq 3 \times \text{ULN}$ will be provided.

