5.2. General Methods

Except the hypothesis testing for CR/CRI, all analyses will be descriptive.

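### The SAP's rule for strict laboratory inequalities subtracts 0.001 from '>' results as well as '<' results, which places a '>x' result below x; the effect is confined to limits that coincide with a cut-off

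*SAP*

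**What the plan says.** SAP 6.6.3 (Laboratory Data) sets out how non-numeric laboratory results become numbers. "Results collected as strict inequalities", with '>10' and '<10' both given as examples, "will be converted to numeric values subtracting a factor of" 0.001. The value is printed in angle brackets. No adding branch is given for '>'. Results reported as '≥' or '≤' "will be converted to the end point".

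On use, the SAP says: "These numeric values will be evaluated for clinically significant abnormalities, but will not be included in calculations of summary statistics". The same section states that "laboratory results will be programmatically classified according to NCI-CTCAE version 5.0 grade", and that tests without CTCAE criteria are placed in three groups: "below normal limit, within normal limits, and above normal limits". It also tabulates liver tests against multiples of the ULN, including ALT or AST of at least 3, 5, 10 and 20×ULN, total bilirubin of at least 2×ULN, and alkaline phosphatase above, or at or below, 2×ULN.

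SAP 5.2 frames all of this as descriptive: "Except the hypothesis testing for CR/CRI, all analyses will be descriptive".

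**The concern.** The only job of a 0.001 offset is to put a censored value on the correct side of a cut-off. For '<x' the true value lies below x, so subtracting is right. For '>x' it lies above x, so subtracting gives a number that the laboratory has ruled out. The rule therefore fails for one of the two directions it names, and it fails precisely where the offset matters, which is when x is itself a cut-off.

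At stake is the programmed classification of laboratory abnormalities, which belong to the secondary safety endpoints in both documents. Grading uses local laboratory results, and SAP 5.2.2 expects many centres, so reporting formats may differ between sites. A programmer who follows the sentence gets wrong classifications at coinciding limits. One who silently corrects it departs from the SAP, and SAP section 2 asks for deviations to be described in the study report.

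**Working it through.** **Inputs.** From SAP 6.6.3: the offset of 0.001, the single operation (subtract) for strict inequalities, the end-point rule for non-strict ones, and the ALT category of at least 3×ULN. The SAP states no converted value, so there is no figure of its own to reproduce. ULN values are not in the documents; 30, 40 and 50 U/L are assumed below for illustration.

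**Step 1: the rule applied to the SAP's own example.** Literal rule: strict inequality at x gives x − 0.001; non-strict gives x. Direction-specific rule: '>x' gives x + 0.001; '<x' gives x − 0.001; non-strict gives x.

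| Reported | Literal SAP rule | Direction-specific rule |
|---|---|---|
| '<10' | 10 − 0.001 = 9.999 | 10 − 0.001 = 9.999 |
| '≤10' | 10 | 10 |
| '≥10' | 10 | 10 |
| '>10' | 10 − 0.001 = 9.999 | 10 + 0.001 = 10.001 |

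Under the literal rule '>10' equals '<10' and ranks below '≥10'. Under the direction-specific rule the order is correct: '<10', then '≤10' and '≥10' together, then '>10'.

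**Step 2: a limit that coincides with a cut-off.** Take ALT reported as greater than exactly 3×ULN, and assume that the converted value feeds the liver categories.

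| Assumed ULN (U/L) | Reported | Literal value ÷ ULN | At least 3×ULN? | With + 0.001 |
|---|---|---|---|---|
| 30 | '>90' | 89.999 ÷ 30 = 2.99997 | No | Yes |
| 40 | '>120' | 119.999 ÷ 40 = 2.99998 | No | Yes |
| 50 | '>150' | 149.999 ÷ 50 = 2.99998 | No | Yes |

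**Step 3: limits that do not coincide.** At an assumed ULN of 40 the cut-off is 3 × 40 = 120.

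| Reported | Literal value | Meets 120? | With + 0.001 | Meets 120? |
|---|---|---|---|---|
| '>119' | 118.999 | No | 119.001 | No |
| '>120' | 119.999 | No | 120.001 | Yes |
| '>121' | 120.999 | Yes | 121.001 | Yes |
| '>500' | 499.999 | Yes | 500.001 | Yes |

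Only the coinciding limit changes.

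**Step 4: direction of the table error.** The number always moves down, but the classification can err either way. A result reported as greater than the ULN is scored within normal limits. One reported as greater than the lower limit of normal is scored below normal. Alkaline phosphatase reported as greater than 2×ULN becomes 2×ULN − 0.001 and moves from the row above 2×ULN to the row at or below it.

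**The case against.** The strongest reply is that no affected record is shown, and that stands. Neither document gives a reporting limit for any analyte. ULN multiples depend on each local laboratory's range, so a match with a '>' limit would be incidental. The 10 in the SAP only illustrates notation; calling it an ULN would be an assumption.

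It also stands that important liver signals have other routes. Protocol 8.3.4 has investigators record clinically significant laboratory changes as adverse events. Protocol 8.4.8 requires notification of Hy's law and potential VOD/SOS cases within 24 hours, Appendix 5 makes potential Hy's law cases SAEs, and the hepatic committee reviews both types (8.3.5, 9.5.2). None of this depends on the 0.001 rule, although none of it repairs the programmed tables.

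The sentence may be a drafting slip: the bracketed 0.001 looks like a template field left in place. That does not rescue it, because the word for subtraction is explicit whatever the size of the factor.

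A reader might go further and infer that a censored eGFR such as '>60' would be graded as reduced kidney function. The documents do not support that. Protocol Table 10 lists creatinine, not eGFR; Appendix 12 calculates eGFR by equation; and the grade cut-offs are not in the documents.

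**Conclusion.** The rule is wrong as written for '>' results, and nothing elsewhere in the SAP or protocol corrects it. The practical effect is probably small and cannot be sized, because the number of reporting limits that coincide with a normal limit, an ULN multiple or a grade cut-off is not given. Where a limit coincides, the '>' result falls on the wrong side of the cut-off; where it does not, the classification is unaffected. The ALT example rests on an assumed ULN and on the converted value being used in the liver categories, which the SAP implies but does not state for those tables.

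A reader might infer that '>' results are misclassified generally, or that the trial's safety or efficacy conclusions are at risk. The documents do not support either inference. The reach is limited to descriptive abnormality categories and shift tables. Converted values are kept out of summary statistics, and the CR/CRi test does not use them. Severity: minor.

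**What to change.** Replace the conversion sentence in SAP 6.6.3 with: 'Results reported as <x are set to x minus 0.001 and results reported as >x are set to x plus 0.001, applied in the reported unit before conversion to SI units.' Remove the angle brackets, and leave the rule for '≥' and '≤' as it is.

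The clause on units is needed because the section converts results to SI units for grading but does not say whether the 0.001 is applied before or after that step.

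The cost is one SAP sentence and one line of code. No data collection, sample size or primary analysis changes.

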#### Type of Participant and Disease Characteristics:

2. Relapsed or refractory CD22-positive ALL ( $\geq 5\%$  marrow blasts, assessed by morphology) due to receive either salvage 1 or salvage 2 therapy and for which treatment with inotuzumab ozogamicin offers a reasonable treatment option.
3. Ph+ ALL patients must have failed treatment with at least 1 tyrosine kinase inhibitor and standard multi-agent induction chemotherapy.
4. Patients in Salvage 1 with late relapse should be deemed poor candidates for reinduction with initial therapy.
5. Patients with lymphoblastic lymphoma and bone marrow involvement  $\geq 5\%$  lymphoblasts by morphologic assessment.
6. ECOG performance status 0-2.
7. Adequate liver function, including total serum bilirubin  $\leq 1.5 \times$  ULN unless the patient has documented Gilbert syndrome, and aspartate and alanine aminotransferase (AST and ALT)  $\leq 2.5 \times$  ULN. If organ function abnormalities are considered due to tumor, total serum bilirubin must be  $\leq 2 \times$  ULN and AST/ALT  $\leq 2.5 \times$  ULN.
8. Serum creatinine  $\leq 1.5 \times$  upper limit of normal (ULN) or any serum creatinine level associated with a measured or calculated creatinine clearance of  $\geq 40$  mL/min.
9. Male and female patients of childbearing potential and at risk for pregnancy must agree to use a highly effective method of contraception throughout the study and for a minimum of 8 months (females) and 5 months (males) after the last dose of assigned treatment. A patient is of childbearing potential if, in the opinion of the Investigator,

he/she is biologically capable of having children and is sexually active. Female subjects of nonchildbearing potential must meet at least 1 of the following criteria:

- a. Achieved postmenopausal status, defined as follows: cessation of regular menses for at least 12 consecutive months with no alternative pathological or physiological cause; and have a serum follicle stimulating hormone (FSH) level confirming the postmenopausal state;
- b. Have undergone a documented hysterectomy and/or bilateral oophorectomy;
- c. Have medically confirmed ovarian failure.

All other female subjects (including female subjects with tubal ligations) are considered to be of childbearing potential.

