## 10.5. Appendix 5: Liver Safety: Suggested Actions and Follow-up Assessments

### Potential Cases of Drug Induced Liver Injury

Humans exposed to a drug who show no sign of liver injury (as determined by elevations in transaminases) are termed “tolerators,” while those who show transient liver injury, but adapt are termed “adaptors.” In some participants, transaminase elevations are a harbinger of a more serious potential outcome. These participants fail to adapt and therefore are “susceptible” to progressive and serious liver injury, commonly referred to as drug induced liver injury (DILI). Participants who experience a transaminase elevation above 3 times the  $\times$  ULN should be monitored more frequently to determine if they are an “adaptor” or are “susceptible.”

In the majority of DILI cases, elevations in AST and/or ALT precede total bilirubin (TBili) elevations ( $>2 \times$  ULN) by several days or weeks. The increase in TBili typically occurs while AST/ALT is/are still elevated above  $3 \times$  ULN (ie, AST/ALT and TBili values will be elevated within the same laboratory sample). In rare instances, by the time TBili elevations are detected, AST/ALT values might have decreased. This occurrence is still regarded as a potential DILI. Therefore, abnormal elevations in either AST OR ALT in addition to TBili that meet the criteria outlined below are considered potential DILI (assessed per Hy’s law criteria) cases and should always be considered important medical events, even before all other possible causes of liver injury have been excluded.

The threshold of laboratory abnormalities for a potential DILI case depends on the participant’s individual baseline values and underlying conditions. Participants who present with the following laboratory abnormalities should be evaluated further as potential DILI (Hy’s law) cases to definitively determine the etiology of the abnormal laboratory values:

- Participants with AST/ALT and TBili baseline values within the normal range who subsequently present with AST OR ALT values  $\geq 3 \times$  ULN AND a TBili value  $\geq 2 \times$  ULN with no evidence of hemolysis and an alkaline phosphatase value  $<2 \times$  ULN or not available.

For participants with baseline AST OR ALT OR TBili values above the ULN, the following threshold values are used in the definition mentioned above, as needed, depending on which values are above the ULN at baseline:

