- Preexisting AST or ALT baseline values above the normal range: AST or ALT values  $\geq 2$  times the baseline values AND  $\geq 3 \times$  ULN; or  $\geq 8 \times$  ULN (whichever is smaller).
- Preexisting values of TBili above the normal range: TBili level increased from baseline value by an amount of  $\geq 1 \times$  ULN or if the value reaches  $\geq 3 \times$  ULN (whichever is smaller).

Rises in AST/ALT and TBili separated by more than a few weeks should be assessed individually based on clinical judgment; any case where uncertainty remains as to whether it represents a potential Hy's law case should be reviewed with the sponsor.

The participant should return to the investigator site and be evaluated as soon as possible, preferably within 48 hours from awareness of the abnormal results. This evaluation should include laboratory tests, detailed history, and physical assessment.

In addition to repeating measurements of AST and ALT and TBili for suspected cases of Hy's law, additional laboratory tests should include albumin, creatine kinase (CK), direct and indirect bilirubin, GGT, PT/international normalized ratio (INR), total bile acids, and alkaline phosphatase. Consideration should also be given to drawing a separate tube of clotted blood and an anticoagulated tube of blood for further testing, as needed, for further contemporaneous analyses at the time of the recognized initial abnormalities to determine etiology. A detailed history, including relevant information, such as review of ethanol, acetaminophen (either by itself or as a coformulated product in prescription or over-the-counter medications), recreational drug, supplement (herbal) use and consumption, family history, sexual history, travel history, history of contact with a jaundiced person, surgery, blood transfusion, history of liver or allergic disease, and potential occupational exposure to chemicals, should be collected. Further testing for acute hepatitis A, B, C, D, and E infection and liver imaging (eg, biliary tract) and collection of serum sample for acetaminophen drug and/or protein adduct levels may be warranted.

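### The SAP's count of possible Hy's law cases uses same-date pairing and fixed ULN multiples, so it can differ in either direction from the protocol's Appendix 5 definition

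*SAP*

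**What the plan says.** **SAP 6.6.3 (Laboratory Data).** The combined liver categories are built from unadjusted ULN multiples. The row closest to Hy's law is "Concurrent (ALT or AST) $\geq 3 \times \text{ULN}$ and TBILI $\geq 2 \times \text{ULN}$ and ALP $\leq 2 \times \text{ULN}$ or missing". Concurrency is then defined: "Concurrent measurements are those occurring on the same date". The section adds that liver function elevations and possible Hy's "Law cases will be summarized using frequency counts and percentages". No other derivation of a possible Hy's law case is given.

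**Protocol Appendix 5 (Liver Safety).** For patients with normal baseline values the criterion is AST or ALT at least 3 × ULN and bilirubin at least 2 × ULN, with no sign of hemolysis and ALP below 2 × ULN or not available. Two further rules have no counterpart in the SAP:

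- Baseline: "For participants with baseline AST OR ALT OR TBili values above the ULN, the following threshold values are used". For AST or ALT this is at least twice baseline and at least 3 × ULN, or at least 8 × ULN, whichever is smaller. For bilirubin it is "TBili level increased from baseline value by an amount of" at least 1 × ULN, or a value of at least 3 × ULN, whichever is smaller.
- Timing: in rare instances, "by the time TBili elevations are detected, AST/ALT values might have decreased. This occurrence is still regarded as a potential DILI". Rises more than a few weeks apart are left to clinical judgment.

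**Protocol 5.1, inclusion criterion 7.** AST and ALT may be up to 2.5 × ULN at entry. Bilirubin may be up to 1.5 × ULN, with documented Gilbert syndrome exempt. The tumor-related exception reads "If organ function abnormalities are considered due to tumor, total serum bilirubin must be" no more than 2 × ULN.

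**The concern.** The two documents attach the same name to differently defined cases, and the SAP neither mentions nor justifies the difference. Hepatotoxicity is a prominent risk of this drug. Protocol 8.4.8 lists Hy's law cases for immediate notification, Appendix 5 has them reported as SAEs, and Protocol 8.3.5 sends them to the HEAC. If the study report tabulates possible Hy's law cases by another rule, its count may not match the SAE and committee case lists, and a reader could not tell whether the gap reflects adjudication or programming.

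**Working it through.** The plan states no expected number of Hy's law cases, so there is no figure to reproduce. The check sets the two rules side by side. All values are in multiples of ULN, and b is the baseline value.

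**Step 1. Thresholds.**

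- Protocol, AST/ALT: 3 if b ≤ 1; otherwise min(max(2b, 3), 8).
- Protocol, bilirubin: 2 if b ≤ 1; otherwise min(b + 1, 3).
- SAP: AST/ALT 3 and bilirubin 2, whatever the baseline.

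| Analyte | Baseline | Protocol threshold | SAP threshold |
|---|---|---|---|
| AST/ALT | up to 1.5 | 3.0 | 3 |
| AST/ALT | 1.6 | 3.2 | 3 |
| AST/ALT | 2.0 | 4.0 | 3 |
| AST/ALT | 2.5 (entry limit) | 5.0 | 3 |
| Bilirubin | up to 1.0 | 2.0 | 2 |
| Bilirubin | 1.2 | 2.2 | 2 |
| Bilirubin | 1.5 (general entry limit) | 2.5 | 2 |
| Bilirubin | 2.0 (entry limit if due to tumor) | 3.0 | 2 |

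**Step 2. Direction of error.** For b > 1 the AST/ALT threshold is the smaller of two values that are each at least 3, so it is never below 3. The bilirubin threshold is the smaller of b + 1 and 3, both above 2, so it is always above 2. The SAP multiples are therefore never stricter than the protocol's, and on their own can only over-count. Same-date pairing is an added restriction, and on its own can only miss cases.

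**Step 3. Test cases** (ALP below 2 and no hemolysis in each).

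1. Baseline normal. ALT is 5 on one visit; a week later bilirubin is 2.5 and ALT has fallen to 2.5. Protocol: case. SAP: no case, because no single date has both elevations.
2. Baseline ALT 2.4, bilirubin normal. Later ALT 3.2 and bilirubin 2.1 on one date. Protocol: no case, because ALT must reach 2 × 2.4 = 4.8. SAP: case.
3. Baseline bilirubin 1.4, ALT normal. Later bilirubin 2.1 and ALT 3.5 on one date. Protocol: no case, because bilirubin must reach 1.4 + 1 = 2.4. SAP: case.

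The baselines in cases 2 and 3 are within criterion 7. With normal baselines and both elevations in one sample the rules agree, except that the SAP row has no hemolysis exclusion and includes ALP of exactly 2 × ULN.

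**Step 4. Size.** With 44 treated patients (SAP 5.1.1), one misclassified patient moves the rate by 1/44 = 2.3 percentage points.

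**The case against.** The strongest reply is that the mismatch is narrow. Appendix 5 itself says that bilirubin typically rises while transaminases are still raised, so that "AST/ALT and TBili values will be elevated within the same laboratory sample". ALT, AST, bilirubin and ALP belong to one chemistry panel (Protocol Table 10), scheduled on Days 1, 8 and 15 of each cycle and at end of treatment, so same-date pairing captures the usual case. This stands, and it limits how often a miss can occur.

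Safeguards also exist. SAP 6.6.3 plans a plot of peak transaminase against peak bilirubin, with no same-date condition, and a listing of all four analytes for anyone crossing any one of the AST, ALT or bilirubin limits. SAE reporting and HEAC review follow the protocol. A reader might infer that liver cases would go unseen; these provisions rule that out. None of them supplies the count, however. The plot's reference lines are fixed at 3 × and 2 × ULN, and the listing classifies no one. Protocol-defined cases would enter the serious-event and serious-hepatotoxicity summaries, but by preferred term among other liver events. The SAP's list of events of special interest has no Hy's law item, and SAP 2.2 mentions its committee only in relation to VOD/SOS.

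Finally, Appendix 5 is clinical guidance. It also calls for repeat testing and for no other reason having been found, and it sets no numeric window, while the SAP rows are a programmed screen. This is fair: no laboratory-derived flag can be guaranteed to match the committee's list. It supports labelling the rows as a screen and showing reviewed cases separately, but it does not justify leaving the baseline and timing rules out without saying so.

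**Conclusion.** The point holds as a defect in one tabulated safety count. The SAP rule can miss staggered cases and can over-count patients with raised baselines (AST/ALT above 1.5 × ULN or bilirubin above ULN), so the table can disagree with protocol-defined cases. Each misclassified patient is worth 2.3 points if 44 are treated. How many patients would be affected cannot be derived from the documents. Efficacy results and case detection are not affected.

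A reader might go further in two ways that the documents do not support.

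- That the table *will* err both ways. Misses need a pattern the protocol calls rare. Over-counts mainly need a raised baseline plus the other elevation on the same date. A patient entering with bilirubin 1.9 × ULN meets the SAP bilirubin limit after a rise of 0.1, against a protocol threshold of 2.9, but that alone is not a counted case.
- That about 2 cases are expected, so that one error could halve or double the count. Protocol 2.2.2.1.3.1 reports Grade 3/4 ALT in 7/161 and bilirubin in 8/161, which scale to 44 × 7/161 = 1.9 and 44 × 8/161 = 2.2 patients. These are single-test rates; no rate of joint elevation is given.

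**What to change.** In SAP 6.6.3, derive the possible Hy's law flag from Appendix 5:

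- use its baseline-dependent AST/ALT and bilirubin thresholds and its ALP condition;
- pair the elevations within a prespecified window chosen and stated by the sponsor, since Appendix 5 offers only a few weeks as a guide.

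Keep the same-date, fixed-multiple rows, labelled as a biochemical screen, and tabulate the HEAC-reviewed Hy's law cases beside them. Align the SAP's description of the committee with the protocol, which includes Hy's law in its remit.

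The cost is SAP wording and minor programming; the laboratory values are already collected. Counts may rise or fall slightly against the present rule.
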